#### **5.6.4 Selection of Doses in the Study**

In a recent Phase 1 study (Study SCRX16-001) with rovalpituzumab tesirine, the maximum tolerated dose (MTD) was established at 0.4 mg/kg every 3 weeks based on the incidence of Cycle 1 toxicities, while the recommended Phase 2 dose (RPTD) in SCLC was chosen as 0.3 mg/kg every 6 weeks for a total of two doses with the allowance to retreat at the same dose level and schedule upon progression. The RPTD is based on the toxicity and efficacy profile during multiple cycles of dosing (AbbVie Stemcentrx data on file).

The chosen dose regimen, two doses of 0.3 mg/kg rovalpituzumab tesirine administered 6 weeks apart, is based on the safety and efficacy observed in Study SCRX16-001, where delayed and/or cumulative toxicities were observed with both q3wk and q6wk schedules and appeared to be related to total dose administered. The dosing regimens of 0.2 mg/kg q3wk for a total of 3 doses (q3wk × 3) and 0.3 mg/kg q6wk for a total of 2 doses (q6wk × 2) were evaluated in expansion cohorts.

Both regimens were tolerated, but the 0.3 mg/kg q 6wk regimen demonstrated a trend towards lower rates of treatment-emergent adverse events (TEAE), related TEAEs, Grade 3/4 TEAEs and related Grade 3/4 TEAEs. In addition, although the 0.3 mg/kg regimen appeared to have a higher incidence of Grade 3/4 thrombocytopenia, this AE was generally clinically manageable. On the other hand, objective responses appear to be more durable in subjects treated with the 0.3 mg/kg q6wk regimen based on preliminary data. Therefore, 0.3 mg/kg q6wk × 2 is the chosen dose regimen for this study. The maximum dose of rovalpituzumab tesirine in this study will not exceed 0.3 mg/kg at each dose.

The starting dose of topotecan is 1.5 mg/m^2 administered intravenously daily for 5 consecutive days starting on Day 1 of a 21-day cycle. Topotecan may be administered at a lower dose if required by the local label. Subjects may continue receiving topotecan until disease progression, unacceptable toxicity, or other reason for study discontinuations.

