5.2 Design Diagram

This is a Phase 3, randomized, open-label, multinational, and multicenter study comparing the efficacy, safety and tolerability of rovalpituzumab tesirine versus topotecan in subjects with advanced or metastatic DLL3^{high} SCLC who have first disease progression during or following front-line platinum-based chemotherapy. DLL3^{high} is defined as $\geq 75\%$ tumor cells staining positive according to the VENTANA DLL3 (SP347) IHC Assay.

Eligible subjects will be randomized in a 2:1 ratio to receive rovalpituzumab tesirine (Arm A) or topotecan (Arm B):

[figure not shown]
- Subjects assigned to Arm A will receive 0.3 mg/kg rovalpituzumab tesirine (IV) on Day 1 of a 42-Day cycle for 2 cycles, along with 8 mg orally (PO) of dexamethasone twice daily on Day –1, Day 1, and Day 2. Regimen of Arm A will be administered for the 2 cycles planned unless earlier discontinuation is warranted due to disease progression, unacceptable toxicity or any other

reason. Up to two additional cycles of rovalpituzumab tesirine may be permitted for subjects in Arm A meeting certain criteria, as described in Section 5.3.1.1 of the study protocol.

- Arm B subjects will receive 1.5 mg/m² topotecan (IV) on Days 1 – 5 of each 21-Day cycle. Topotecan may be administered at a lower dose if required by the local label. The Arm B regimen will be administered until disease progression, unacceptable toxicity or any other reason requiring treatment discontinuation.

A schematic of the study is provided in Figure 1 Study Schema.

Figure 1. Study Schema

Empty arrowhead = Rovalpituzumab tesirine administration cycle; Dotted arrowhead = Additional Rovalpituzumab tesirine administration cycle; Filled arrowhead = Topotecan administration cycle; PTFU = post-treatment follow-up; OS = overall survival

1. Tumor material collection and testing for DLL3 status may occur at any time after initial diagnosis, including outside of the Screening window, depending on completion of the appropriate consent process.
2. Up to two additional cycles of rovalpituzumab tesirine may be permitted for subjects in Arm A meeting certain criteria, as described in Protocol Section 5.3.1.1.
3. Topotecan will be administered until disease progression, unacceptable toxicity or any other reason requiring treatment discontinuation.

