10.0 Study Drug

10.1 Study Drug Exposure

Summary of study drug exposure will be presented on the safety set.

The following summaries will be presented by treatment group:

- The number and percentage of subjects with total number of cycles of rovalpituzumab tesirine and topotecan received,
- Descriptive summary of average dose level per cycle (mg/kg for rovalpituzumab tesirine; mg for dexamethasone; mg/m² for topotecan),

An overview of interruption and dose reduction will be presented for each of rovalpituzumab tesirine, dexamethasone, and topotecan treatments as following:

- The number and percentage of subjects who had at least one interruption of study drug (rovalpituzumab tesirine/dexamethasone/topotecan) administration, and further breakdowns by the number of interruptions and by reason,
- The number and percentage of subjects who had at least one dose reduction, and further breakdowns by the number of dose reductions and by reason.

For each cycle, the number and percentages of subjects with interruption and reason will be presented (42-day cycle for rovalpituzumab tesirine; 21-day cycle for topotecan). Similarly, the number and percentages of subjects with dose reduction and reason will be presented at each cycle.

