12.2 Analysis of Adverse Events

Adverse Event Overview

The number and percentage of subjects experiencing TEAEs between the treatment groups will be summarized for the following adverse event categories.

- TEAEs
- NCI toxicity (maximum) grade 3 or 4 TEAEs
- Drug-related TEAEs
- NCI toxicity (maximum) grade 3 or 4 drug-related TEAEs
- Serious TEAEs
- NCI toxicity (maximum) grade 3 or 4 serious TEAEs

- Drug-related serious TEAEs
- TEAEs leading to discontinuation/reduction/interruption of study drug,
- Drug-related TEAEs leading to discontinuation/reduction/interruption of study drug
- TEAEs leading to death
- Drug-related TEAEs leading to death

Adverse Events by System Organ Class and Preferred Term

The number and percentage of subjects experiencing TEAEs will be tabulated according to the primary MedDRA system organ class (SOC) and MedDRA preferred term (PT) for each treatment group. Subjects reporting more than one adverse event for a given MedDRA PT will be counted only once for that term. Subjects reporting more than one type of adverse event within a MedDRA SOC will be counted only once for that SOC. Subjects reporting more than one type of adverse event will be counted only once in the overall total.

AEs by Preferred Term

The number and percentage of subjects experiencing adverse events will be tabulated according to the MedDRA PT for each treatment group. Subjects reporting more than one AE for a given MedDRA PT will be counted only once for that term.

AEs by Maximum Severity

Adverse events will be summarized by SOC, PT and maximum severity per NCI CTCAE v.4 grading in each treatment arm. If a subject has an AE with unknown severity, then the subject will be counted in the severity category of "unknown," unless the subject does not have another occurrence of the same AE with a severity present. In addition, Grade 3 or higher AE will also be summarized by SOC and PT.

AEs by Relationship

Adverse events possibly related to rovalpituzumab tesirine, dexamethasone, topotecan, as assessed by the investigator, will be summarized separately in each treatment arm.

Following summaries will be presented for the AEs possibly related to rovalpituzumab tesirine, dexamethasone, topotecan, separately:

- Summary of AE by PT
- Summary of AE by SOC and PT
- Summary of Grade 3 or higher AE by SOC and PT
- Summary of SAE by SOC and PT
- Summary of rovalpituzumab tesirine discontinuation by SOC and PT (possibly related to rovalpituzumab tesirine only)

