12.3.1 SAEs (Including Deaths) and Adverse Events Leading to Study Drug Discontinuation

SAEs and AEs leading to rovalpituzumab tesirine, dexamethasone, topotecan, dose reduction and dose interruption will be summarized separately by SOC and PT in each treatment arm. Separate listings for SAEs, AEs leading to death and AEs leading to treatment discontinuation will also be provided.

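### The SAP 12.2 rows for TEAEs leading to discontinuation, reduction or interruption are not comparable between arms, because Arm A has far fewer dose decisions at which such an action can be recorded

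*SAP*

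**What the plan says.** The adverse event overview in SAP 12.2 sets out its tables as follows: "The number and percentage of subjects experiencing TEAEs between the treatment groups will be summarized for the following adverse event categories". One category is "TEAEs leading to discontinuation/reduction/interruption of study drug", and there is a drug-related version. Each subject counts once. SAP 12.1 sets the TEAE window at first dose to 70 days after the last dose, in both arms. No adjustment for exposure, cycles or doses due is given.

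Two related outputs count in the same way:

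- SAP 10.1 gives "The number and percentage of subjects who had at least one dose reduction", with a matching line for interruptions.
- SAP 12.3.1 states: "SAEs and AEs leading to rovalpituzumab tesirine, dexamethasone, topotecan, dose reduction and dose interruption will be summarized separately by SOC and PT".

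The regimens differ in structure. Under SAP 5.2, Arm A receives "rovalpituzumab tesirine (IV) on Day 1 of a 42-Day cycle for 2 cycles", and "Up to two additional cycles of rovalpituzumab tesirine may be permitted for subjects in Arm A meeting certain criteria". Arm B receives topotecan on five days of every 21-day cycle, with no fixed number of cycles, until progression, toxicity or another reason to stop.

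On the experimental drug's toxicity in the Phase 1 study, Protocol 5.6.4 reports that "delayed and/or cumulative toxicities were observed with both q3wk and q6wk schedules and appeared to be related to total dose administered".

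**The concern.** A subject can enter these rows only if a dose is there to be delayed, reduced, interrupted or withheld. In the planned course an Arm A subject has one between-dose decision, at about Rx Day 43. A toxicity that starts after dose 2 usually has no planned dose left to change, so it usually leaves no trace in these rows. An Arm B subject faces a new decision every three weeks while on treatment. The protocol describes the experimental drug's toxicity as delayed or cumulative and related to total dose, so the period with little opportunity for action is one in which toxicity is expected.

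Comparing safety and tolerability with topotecan is a stated objective (Protocol 4.0, SAP 5.1.3). If these percentages are read side by side, part of any difference reflects how many doses were scheduled, not how well each drug was tolerated.

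**Working it through.** The documents give no expected figure for these rows, so there is none to reproduce. The check asks what the row would show if underlying risk were the same in both arms.

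**Inputs**

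- Arm A: decision before Cycle 2, 42 days after dose 1 (SAP 5.2).
- Arm A retreatment: up to two more cycles, requiring among other criteria progression at least 12 weeks after dose 2 (Protocol 5.3.1.1), so about 42 + 84 = 126 days after dose 1.
- Arm B: one decision per 21 days while progression-free (SAP 5.2).
- Median PFS: 2.7 months for topotecan (Protocol 3.1), or 2.7 × 30.4375 = 82.2 days, applied to both arms. Sensitivity value for Arm A: 3.9 months, from the third-line Phase 2 study (Protocol 3.3).
- Assumptions not in the documents: exponential time to progression, and a risk p of an AE-driven action of 5% to 20% per decision.

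**Progression-free probabilities**, S(d) = 2^(−d/82.2): S(21) = 0.838, S(42) = 0.702, S(126) = 0.346.

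**Decisions per subject**

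- Arm B mean: S(21) / (1 − S(21)) = 5.2. A subject at the median has started four cycles, so has had three between-cycle decisions.
- Arm A mean: 0.70 without retreatment. If everyone who meets the timing criterion takes both extra cycles: 0.702 + 2 × 0.346 = 1.39.

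**Row percentage**

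- Arm B: 1 − (1 − S(21)) / (1 − S(21)(1 − p)).
- Arm A, no retreatment: S(42) × p.
- Arm A, all time-eligible subjects retreated: (S(42) − S(126)) × p + S(126) × (1 − (1 − p)³).
- For equal weekly risk, Arm A's p is replaced by 1 − (1 − p)², since its decision covers 42 days.

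Arm A ranges run from no retreatment to all time-eligible subjects retreated.

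| p per 21 days | Arm B | Arm A, equal risk per decision | Arm A, equal weekly risk |
|---|---|---|---|
| 5% | 20.5% | 3.5-6.7% | 6.8-12.6% |
| 10% | 34.0% | 7.0-12.9% | 13.3-23.0% |
| 20% | 50.8% | 14.0-24.0% | 25.3-38.3% |

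**Sensitivity.** With Arm A's median PFS at 3.9 months, S(42) = 0.783 and S(126) = 0.479. With all time-eligible subjects retreated and p = 10%, Arm A shows 16.0% at equal per-decision risk. At equal weekly risk it shows (0.783 − 0.479) × 0.19 + 0.479 × (1 − 0.81³) = 28.2%. Both are still below 34.0%. With a 2.7-month median in both arms, equal rows would need Arm A's per-decision risk to be about 2.7 to 5.9 times Arm B's.

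**Check of an equal-time comparison.** Take p = 10% per 21 days, equal weekly risk, and only TEAEs with onset in Rx Days 1-42. Arm A shows 0.702 × 0.19 = 13.3%. Arm B, with decisions at 21 and 42 days, shows (0.838 − 0.702) × 0.10 + 0.702 × 0.19 = 14.7%. The structural gap almost closes.

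**The case against.** A reader might infer that Arm A can register only one dose decision, that no event after dose 2 can ever enter the rows, and that rovalpituzumab tesirine must therefore look more tolerable by construction. The documents do not support that reading.

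- Retreated subjects have further decisions. The number is unknown: about 35% meet the timing criterion under the assumptions above, and the other criteria in Protocol 5.3.1.1 would lower that.
- Protocol 5.5.2 lets each infusion be adjusted to tolerability, and SAP 10.1 counts dexamethasone interruptions, so a late action is possible, if uncommon.
- Arm B does not register every cycle. Each subject counts once, so more cycles mean more chances to enter the row.
- The triggers differ. Reductions under protocol Table 6 are mandatory and include Grade 2 effusion or edema, while Arm B follows the local label (Protocol 5.5.6.1.3). Arm A's risk per decision could be much higher.
- The 70-day tail is not peculiar to Arm A. For a two-dose Arm A subject, 70 of 113 window days (62%) follow dose 2. A topotecan subject progressing at Day 82 after a last dose on Day 68 has a window to Day 138, of which 56 to 70 days (41-51%) also follow the last possible action.
- The model doses Arm B until progression and ignores stops for other reasons, which overstates its decisions. It also leaves out topotecan Days 2-5, which understates them.

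The SAP also covers much of the ground elsewhere. SAP 10.1 tabulates interruption and reduction, with reasons, by cycle. Late toxicity is captured in the Grade 3 or 4, serious, drug-related and fatal TEAE rows, and in the AESI outputs with Kaplan-Meier time to onset.

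These points stand. They limit the claim but do not make the crude rows comparable. The by-cycle tables set 42-day cycles beside 21-day cycles and do not include discontinuation.

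**Conclusion.** The concern holds in a limited form. The opportunity to enter these rows differs by design: one planned between-dose decision in Arm A, against three for a topotecan subject at median PFS. At equal underlying risk the crude percentage favours Arm A in every scenario computed. At 10% per 21 days and a 2.7-month median PFS in both arms, it is about 13-23% against 34% at equal weekly risk, and 7-13% against 34% at equal per-decision risk. The size rests on exponential progression and on an assumed action risk that the documents do not give.

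The observed direction cannot be predicted, because the dose-modification rules differ. The conclusion is that these rows do not support a between-arm reading, not that they will favour Arm A. They are descriptive summaries for an exploratory objective. No test, alpha or sample size depends on them, so the priority is minor.

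**What to change.** In SAP 12.2, with matching notes in 10.1 and 12.3.1:

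1. Keep the crude percentages, labelled as within-arm description, and show discontinuation, reduction and interruption as separate rows.
2. For the between-arm reading, add a version limited to actions caused by TEAEs with onset in Rx Days 1-42 in both arms. A dose is scheduled at about Rx Day 43 in each arm (Cycle 2 in Arm A, Cycle 3 in Arm B), so the calendar time matches. A rate per dose due would not serve: it sets 42-day intervals against 21-day intervals, and equal weekly risk would then appear as 19% against 10%, to Arm A's disadvantage.
3. For Arm A, add the number of subjects with a TEAE starting after dose 2 that meets a row of protocol Table 6.

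The cost is one or two extra descriptive tables from data already collected. The equal-time version ignores later Arm B actions, which remain visible in the crude rows. No dosing rule changes. SAP 4.0 describes the plan as a draft to be finalized before any comparison by arm, so the wording can still be added.

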### **6.1 Medical Complaints**

The investigator will monitor each subject for clinical and laboratory evidence of adverse events on a routine basis throughout the study. The investigator will assess and record any adverse event in detail including the date of onset, event diagnosis (if known) or sign/symptom, severity, time course (end date, ongoing, intermittent), relationship of the adverse event to study drug, and any action(s) taken. For serious adverse events considered as having "no reasonable possibility" of being associated with study drug, the investigator will provide another cause of the event. For adverse events to be considered intermittent, the events must be of similar nature and severity. Adverse events, whether in response to a query, observed by site personnel, or reported spontaneously by the subject will be recorded.

All adverse events will be followed to a satisfactory conclusion.

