### 6.1.3 Relationship to Study Drug

The investigator will use the following definitions to assess the relationship of the adverse event to the use of study drug:

Reasonable Possibility	After consideration of factors including timing of the event, biologic plausibility, clinical judgment, and potential alternative causes, there is sufficient evidence (information) to suggest a causal relationship.
No Reasonable Possibility	After consideration of factors including timing of the event, biologic plausibility, clinical judgment, and potential alternative causes, there is insufficient evidence (information) to suggest a causal relationship.

For causality assessments, events assessed as having a reasonable possibility of being related to the study drug will be considered "associated." Events assessed as having no reasonable possibility of being related to study drug will be considered "not associated." In addition, when the investigator has not reported a causality or deemed it not assessable, AbbVie will consider the event associated.

If an investigator's opinion of no reasonable possibility of being related to study drug is given, an "Other" cause of event must be provided by the investigator for the serious adverse event.

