### **8.2.1 Treatment-Emergent Adverse Events (TEAEs)**

TEAEs reported during the study will be coded using a MedDRA dictionary. Incidence of TEAEs will be summarized by treatment arm and the following:

- System organ class and preferred term
- System organ class, preferred term, and severity

These summaries will be presented for the following subsets:

- Serious TEAEs
- All TEAEs
- Drug-related TEAEs

For tables reporting AEs by severity, if a subject has multiple occurrences of an AE with the same organ class and preferred term, the most severe event will be presented.

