For lab and vital sign parameters, the final observation is defined as the last non-missing post-baseline measurement collected not more than 70 days after the last dose of investigational product.

Missing Data

No missing data imputation will be implemented, unless specified otherwise.

Definition of Study Day (Day Relative to the day of Randomization) and Rx Day (Day Relative to the First Dose of Study Drug)

Study Day of any observation is defined for post-randomization observations as:

$$\text{Study Day} = \text{Date of observation} - \text{Date of randomization} + 1,$$

and for observations pre-dating randomization as:

$$\text{Study Day} = \text{Date of observation} - \text{Date of randomization}.$$

Thus, the day of randomization is defined as Study Day 1, while the day prior to the randomization is defined as Study Day -1 (there is no Study Day 0).

Study Rx Day of any post-baseline observation is defined as the number of days from the day of the first dose of any study drug (rovalpituzumab tesirine or topotecan) to the date of observation. It is calculated for each observation as follows:

- Study Rx Day = Date of observation – Date of first dose of any study drug + 1

Definition of Analysis Windows

All time points and corresponding time windows are based on Study Rx Days, unless specified otherwise. For analysis at visit, especially for the laboratory data (hematology, chemistry, and urinalysis), nominal days and visit windows for the 2 treatment arms (Arm A and Arm B) are given in the table below. If more than one observation is included in a time window, the observation closest to the nominal day should be used. If there are two observations equally distant to the nominal day, the later one will be used in analyses.

Table 1. Visit Window laboratory and vital sign analysis

Study Visit (Week)	Nominal Study Rx Day	Time Window (Study Rx Days Range)
Baseline		Baseline definition
3	22	2 to \leq 32
6	43	33 to \leq 53
...
$3 \cdot X$	$7 \cdot 3 \cdot X + 1$	$7 \cdot 3 \cdot X - 9$ to $\leq 7 \cdot 3 \cdot X + 11$

The endpoints based on subject self-reported health related quality of life (QoL) and symptom assessments will be analyzed for post-treatment Week 3, Week 7 and subsequently with the increment of 6 weeks (i.e., Week 13, Week 19, and Week 24). The visit windows for the PRO endpoints are defined in [Table 2](#) below.

Table 2. Visit Window for PRO analysis

Study Visit (Week)	Nominal Study Rx Day	Time Window (Study Rx Days Range)

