- Summary of topotecan discontinuation by SOC and PT (possibly related to topotecan only)

If a subject has an AE with unknown relationship, then the subject will be counted in the relationship category of "unknown," unless the subject does not have another occurrence of the same AE with a relationship present.

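### SAP 12.2 reverses its own counting rule for adverse events of unknown severity or unknown relationship through a double negative

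*SAP*

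**What the plan says.** SAP 12.2, under AEs by Maximum Severity, opens with the aim of the table: "Adverse events will be summarized by SOC, PT and maximum severity per NCI CTCAE v.4 grading in each treatment arm". It then assigns a subject who has an event of unknown severity to an *unknown* category, "unless the subject does not have another occurrence of the same AE with a severity present".

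Under AEs by Relationship, the same section first names whose judgement is used: "Adverse events possibly related to rovalpituzumab tesirine, dexamethasone, topotecan, as assessed by the investigator, will be summarized separately in each treatment arm". It closes with a parallel rule: a subject with an event of unknown relationship is counted as *unknown*, "unless the subject does not have another occurrence of the same AE with a relationship present".

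Three other places bear on the point.

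- Protocol 8.2.1, on severity tables: "if a subject has multiple occurrences of an AE with the same organ class and preferred term, the most severe event will be presented".
- Protocol 6.1.3, on causality: "when the investigator has not reported a causality or deemed it not assessable, AbbVie will consider the event associated".
- SAP 7.0, on missing data: "No missing data imputation will be implemented, unless specified otherwise".

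**The concern.** A rule of the form *count as unknown unless there is no known value* does the opposite of what a maximum-severity table needs. It keeps the subject in *unknown* when a grade is available, and makes the exception when none is.

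The situation can arise in this trial. Protocol 6.1.1.1 and 6.1.2 require a worsening event to be reported as a new event, so one subject may have several records under one preferred term. If one of those records lacks a grade or an attribution, the rule decides which cell the subject occupies.

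At stake is the accuracy of the by-severity and by-relationship safety tables. These remain planned. Protocol 8.0 withdraws statistical testing of the efficacy endpoints after enrolment stopped, but the safety summaries in Protocol 8.2 stand. Overall survival, the type I error rate and the all-event counts by preferred term do not depend on this rule.

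**Working it through.** The plan states no figure to reproduce. The check is one of logic.

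**Form of the rule.** *P unless Q* means: if Q is false, then P. Here P is that the subject is counted as *unknown*. Q is that the subject has no other record of the same event with a known value.

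**Cases for one subject and one preferred term.**

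| Records of the event | Is Q true? | SAP 12.2 read literally | Maximum-severity aim and Protocol 8.2.1 |
|---|---|---|---|
| One ungraded, one Grade 3 | No | *Unknown* | Grade 3 |
| Ungraded only | Yes | Excepted from *unknown*; no category named | *Unknown* (no grade to present) |

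The first row is wrong on any reading of *unless*. The second depends a little on interpretation. If *unless* excludes the subject, the subject has no cell. If it is read as a plain *or*, the cell is undetermined. Neither reading gives a usable rule.

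**Direction.** Take a subject with at least one ungraded record and a set K of known grades. If K is not empty, the literal rule moves the subject from the cell max(K) to *unknown*. If K is empty, the subject was never in a known-grade cell. Known-grade cells can therefore lose subjects and never gain them. The *unknown* cell can move either way: it gains the mixed subjects and may lose the unknown-only ones.

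**Relationship.** The same logic applies. A subject with one related record and one unattributed record is counted as *unknown* under the literal text, although the investigator has called an occurrence related.

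**Check of the correction.** With the stray *not* removed, row one gives Grade 3 and row two gives *unknown*. Both agree with Protocol 8.2.1.

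**Scale per affected subject.** Protocol 8.4 gives 444 enrolled, randomized 2:1. Assume an exact split and that all were dosed. Arm A is then 444 × 2/3 = 296 and Arm B is 444 × 1/3 = 148. One misplaced subject moves a cell by 1/296 = 0.34 percentage points in Arm A or 1/148 = 0.68 in Arm B. This gives the weight of one subject. It does not estimate how many are affected.

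**The case against.** The strongest reply is that this is a drafting slip whose intended meaning is obvious. The sentence before the severity rule states the aim, Protocol 8.2.1 supplies the correct rule, and a competent programmer would follow those. That is fair as to intent. It does not remove the error: a rule that is wrong if followed, and departed from if silently corrected, should be put right.

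The second reply concerns reach, and it stands. The severity sentence belongs to the maximum-severity table. Events of Grade 3 or higher have their own summary in SAP 12.2 and their own listing in SAP 12.3.2, and the overview has its own maximum-grade categories. The SAP attaches the *unknown* rule to none of these. A reader might infer that all high-grade counts are compromised; the documents do not support that.

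The third reply concerns frequency, and it also stands. Protocol 6.1 asks the investigator to record severity and the "relationship of the adverse event to study drug, and any action(s) taken". Protocol 6.1.2 adds a fallback grading for when CTCAE criteria cannot be used. Missing values should be few, and no affected number can be taken from the documents.

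A reader might also infer that the *unknown* relationship category contradicts Protocol 6.1.3. The documents do not show this. Section 6.1.3 says how the sponsor regards an event with missing causality, whereas SAP 12.2 bases its relationship summaries on the investigator's assessment. The two can coexist, and an *unknown* category fits the no-imputation default in SAP 7.0. What remains is a small lack of explicitness, since the drug-related overview categories do not restate their basis.

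Nor does removing the *not* open a demonstrated gap for a subject with unknown, related and not-related records. The listed relationship summaries cover events possibly related to each drug, and such a subject has one.

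**Conclusion.** The point holds as an error of wording in a stated counting rule, made twice. Programmed as written, SAP 12.2 puts subjects with both known and unknown values into *unknown*, and leaves those with only unknown values without a stated category. For severity it contradicts the table's own purpose and Protocol 8.2.1.

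The effect is limited to the by-severity and by-relationship adverse event tables. Its direction for graded cells is fixed: understatement or no change. Its size depends on how many subjects have a missing grade or attribution; the documents do not give that number, and it may be zero. If the programming already follows the evident intent, correcting the text changes no count.

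The relation to Protocol 6.1.3 is a matter for optional clarification and is not part of the error.

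**What to change.** Replace the two sentences in SAP 12.2 with wording to this effect.

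- Severity: *A subject is counted under unknown severity only when no record of that event carries a grade; otherwise the highest recorded grade is used.*
- Relationship: *A subject is counted under unknown relationship only when no record of that event carries an attribution; if any record is assessed as related, the subject is counted as related.*

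The second half of the relationship sentence makes explicit the precedence that summaries of related events already imply.

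Optionally, add one sentence saying that the drug-related summaries use the investigator's assessment, and how missing or non-assessable causality is displayed relative to Protocol 6.1.3.

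The cost is two sentences and a check of the matching table programs. SAP 4.0 describes the document as a draft to be finalized before any comparative analysis by arm, so the change fits that step.
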